**Table 10 Schedule of Activities for Cohorts 4, 5, 6, 8, 7, and 9**

	Screening 	Treatment Period			Early Termination	Safety Follow-up 
		Day 1	Week 2	Week 4 (EOT)		
VISIT NUMBER	1	2	3	4		5
STUDY DAY	≤14 days before V2	1	14	28		Last dose +30 days
Visit windows			±3 days	±3 days		±7 days
Informed consent/assent	X					
Inclusion/exclusion criteria	X	X				
Demography & medical history	X					
Review of prior medications from past year	X					
Review of concomitant medications	X	X	X	X	X	X
Hepatitis B & C and HIV Screening	X					
Pregnancy test for FOCP 	X	X	X	X	X	X 
Laboratory assessments 	X	X	X	X	X	X 
Pharmacodynamics and Tildacerfont Concentration Samples (by Cohort)						
Cohorts 4, 5, 6, and 7 PD markers and tildacerfont concentration (serial, drawn together)  (also 8 and 9 if indicated)		X	X			
Cohorts 4, 5, 6, and 7 PD markers and tildacerfont concentration (single sample)  (also 8 and 9 if indicated)				X	X	X 
A4-based GC dose adjustment 				X		
Weight-based tildacerfont dose adjustment	X					
Urinalysis 	X		X		X	X 
Vital signs  , body weight	X	X	X	X	X	X 
Physical exam 	X	X	X	X	X	X 
12-lead ECG	X		X 		X	X 
Bone age and predicted adult height 	X					

	Screening 	Treatment Period			Early Termination	Safety Follow-up 
		Day 1	Week 2	Week 4 (EOT)		
VISIT NUMBER	1	2	3	4		5
STUDY DAY	≤14 days before V2	1	14	28		Last dose +30 days
Visit windows			±3 days	±3 days		±7 days
C-SSRS 	X		X	X	X	X 
PROMIS 	X		X	X	X	X 
SWYC 	X		X	X	X	X 
Dispense study drug 		X				
Study drug accountability			X	X	X	
Clinic drug administration 			X	X		
Review any AEs			X	X	X	X

Abbreviations: 11KT=11-ketotestosterone; A4=androstenedione; ACTH=adrenocorticotropic hormone; AEs=adverse events; ALT=alanine aminotransferase; ALP=alkaline phosphatase; AST=aspartate aminotransferase; CRO=contract research organization; C-SSRS=Columbia–Suicide Severity Rating Scale; ECG=electrocardiogram; eGFR=estimated glomerular filtration rate; EOT=end of treatment; ET=early termination; FOCP=female of childbearing potential; GC=glucocorticoid; GGT=gamma-glutamyl transferase; HIV=human immunodeficiency virus; EP=open-label extension; PD=pharmacodynamics; PK=pharmacokinetics; PROMIS=Patient Reported Outcomes Measurement Information System; 17-OHP=17-hydroxyprogesterone; SWYC=Survey of Well-being of Young Children; T=testosterone.

 The Screening Period may be extended as approved by the Sponsor or CRO designee.

 For participants continuing in the EP period, the Safety Follow-up Visit will be 30 days after their last dose in the EP Period.

 A pregnancy test will be performed at every visit for FOCP. The Screening Visit will include a serum pregnancy test. All subsequent visits will include urine pregnancy tests. Any positive urine pregnancy test must be followed up by a serum pregnancy test for confirmation.

 Labs will be drawn at approximately 8 AM (±1 h) before any morning dose of GC medication.

 Laboratory assessments include: A4, coagulation panel (Screening only), hematology, chemistry (including liver function tests AST, ALT, ALP, GGT, total and direct bilirubin, and total bile acids), thyroid panel. Fasting is not required.

 As needed based upon safety concerns, per Investigator discretion.

 For Cohorts 4, 5, 6, 8, 7, and 9 serial blood samples at 3 timepoints to assess PD (ACTH, 17-OHP, A4, testosterone, 11KT, cortisol) and tildacerfont concentrations following the morning (1st) dose: pre-dose (prior to GC dosing and tildacerfont dosing), 0.5 to 1.5 hours post GC and tildacerfont dose, and 3 to 5 hours post-GC and tildacerfont dose. Serial samples should be attempted in all cases but may be declined in Cohort 7 & 9 at Investigator's discretion (e.g., unable to establish IV, behavioral challenges impede collection and risk other assessments).

 For Cohorts 4, 5, 6, 8, 7, and 9 single blood sample to assess PD (ACTH, 17-OHP, A4, testosterone, and 11KT) and cortisol and tildacerfont concentration. Pre-dose at approximately 8 AM (±1 h), prior to GC dosing and tildacerfont dosing.

 Tildacerfont concentration collected prior to the morning tildacerfont and GC dose. Fasting is not required.

 In all cohorts, GC dose (frequency or total daily dose) may be adjusted based on A4 levels collected at Week 4 (for those participants continuing in the optional EP). If a change in GC is warranted by the A4 algorithm, sites will contact participants by telephone after receipt of results (within approximately 2 weeks) after each applicable study visit.

 Urinalysis should include the following: specific gravity, pH, glucose, protein, blood, ketones, bilirubin, urobilinogen, nitrite, by dipstick. Microscopic examination should be obtained if blood or protein is abnormal. For visits in which tildacerfont is administered, urinalysis should be performed pre-dose.

 Systolic and diastolic blood pressure, pulse rate, body temperature, and respiration rate. Height will only be collected every 6 months.

 Full physical exam is performed at Visit 2, EOT, and the ET Visit; an abbreviated/directed physical exam is performed at all other visits.

 Day 1 ECGs are conducted pre-dose. Day 14 ECG is dose independent, as participants should be at steady state.

 Historical bone age and predicted adult height calculation may be used if performed  $\leq$ 6 months prior to Screening. If no appropriate image is available, x-ray of left hand and wrist will be performed to assess bone age and calculate predicted adult height. This may not be performed if deemed inappropriate by the investigator (based on maturation level). This will not be performed in adults (Cohorts 4 & 5).

 The C-SSRS, to assess suicidality, is only conducted for participants aged  $\geq$ 6 years.

 PROMIS, to assess anxiety and depression, is conducted for participants aged  $\geq$ 5 years.

 The SWYC to assess anxiety and depression is only conducted in Cohort 7 (and 9 if indicated) for participants  $\leq$ 5 years of age.

 A 4-week supply of study drug will be dispensed at Visit 2 (Day 1). Participants should bring study drug to all visits for accountability. Upon receipt of study drug, the pharmacy will hold/store two doses to ensure that in-clinic dosing can occur at Visit 3 (Week 2) in the event a participant does not bring study drug to the visit.

 All cohorts will dose in clinic with a morning meal for their first dose to allow observation 1 hour post dose.

**Table 11 Schedule of Activities for Extension Period for Cohorts 4, 5, 6, 8, 7, and 9**

	Week 4	Week 8	Week 12	Week 24	Week 36	Week 48	Week 60	Week 72	Week 84	Week 96 (EOT)	Early Termination	Safety Follow-up (Phone call)
VISIT NUMBER	4	5	6	7	8	9	10	11	12	13		
Visit windows	±2 weeks		Last dose +30 days									
Informed consent/assent	X											
Concomitant medications	X	X	X	X	X	X	X	X	X	X	X	X
Pregnancy test for FOCP 	X	X	X	X	X	X	X	X	X	X	X	
Laboratory assessments 	X	X	X	X	X	X	X	X	X	X	X	X 
PD and tildacerfont samples 	X	X	X	X	X	X	X	X	X	X	X	X 
A4-based GC dose adjustment 	X	X	X	X	X	X	X	X	X	X		
Urinalysis 				X		X	X	X	X	X	X	X 
Vital signs  , body weight	X	X	X	X	X	X	X	X	X	X	X	X 
Abbreviated/directed physical exam	X	X	X	X	X	X	X	X	X	X	X	X 
C-SSRS 	X	X	X	X	X	X	X	X	X	X	X	X 
PROMIS 	X	X	X	X	X	X	X	X	X	X	X	X 
SWYC 	X	X	X	X	X	X	X	X	X	X	X	
Bone age and predicted adult height 				X		X		X		X		
Weight/Efficacy Tildacerfont Dose Adjustment	X		X	X	X	X	X	X	X			
Dispense study drug	X	X	X	X	X	X	X	X	X			
Review any AEs	X	X	X	X	X	X	X	X	X	X	X	X
Study drug accountability	X	X	X	X	X	X	X	X	X	X	X	

Abbreviations: 11KT=11-ketotestosterone; A4=androstenedione; ACTH=adrenocorticotropin hormone; AEs=adverse events; ALT=alanine aminotransferase; ALP=alkaline phosphatase; AST=aspartate aminotransferase; C-SSRS=Columbia–Suicide Severity Rating Scale; ECG=electrocardiogram; EOT=end of treatment; ET=early termination; FOCP=female of childbearing potential; GC=glucocorticoid; GGT=gamma-glutamyl transferase; PD=pharmacodynamics; PROMIS= Patient Reported Outcomes Measurement Information System; 17-OHP=17-hydroxyprogesterone; SWYC=Survey of Well-being of Young Children; T=testosterone.

 A serum pregnancy test will be performed at Screening for FOCP only. All subsequent tests will be urine pregnancy tests

 Labs will be drawn at 8 AM ( $\pm 1$  h) before any morning dose of GC medication.

 Laboratory assessments include: hematology, chemistry (including liver function tests AST, ALT, ALP, GGT, total and direct bilirubin, and total bile acids), thyroid panel. Fasting is not required.

 As needed based upon any safety concerns, per Investigator discretion.

 PD Samples (ACTH, 17-OHP, A4, testosterone, and 11KT). They must be drawn prior to GC dosing. Fasting is not required. Single samples for plasma concentration of tildacerfont will be drawn at all visits.

 GC dose (frequency or total daily dose) may be adjusted based on A4 levels collected at each visit. If a change in GC is warranted by the A4 algorithm, sites will contact participants by telephone after receipt of results (within approximately 2 weeks) after each applicable study visit.

 Urinalysis should include the following: specific gravity, pH, glucose, protein, blood, ketones, bilirubin, urobilinogen, nitrite, by dipstick. Microscopic examination should be obtained if blood or protein is abnormal.

 Systolic and diastolic blood pressure, pulse rate, body temperature, and respiration rate.

 The C-SSRS, to assess suicidality, is only conducted for participants aged  $\ge 6$  years.

 PROMIS, to assess anxiety and depression, is conducted for participants aged  $\ge 5$  years.

 The SWYC to assess anxiety and depression is only conducted in Cohort 7 (and 9 if indicated) for participants  $\le 5$  years of age.

 Historical bone age and predicted adult height calculation will be performed by an x-ray of left hand and wrist to assess bone age and calculate predicted adult height. This may not be performed if deemed inappropriate by the investigator (based on maturation level). This will not be performed in adults (Cohorts 4 & 5).

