3.1.2.4. Visit 4 (Week 4 ± 3 days) (EOT for Cohorts 4-9)

Visit 4 will be conducted as an outpatient visit. The following activities will be conducted:

- Review concomitant medications for any changes
- Pregnancy test for FOCP (urine)
- Safety labs (see [Appendix 1](#) and [Appendix 3](#))
- Pharmacodynamics (ACTH, 17-OHP, A4, testosterone, and 11KT) drawn prior to GC dosing at approximately 8 AM (± 1 hour). Fasting is not required.
- Cortisol
- Tildacerfont concentration (single sample) drawn prior to GC dosing at approximately 8 AM (± 1 hour). Fasting is not required.
- GC dosing adjustments to be determined after A4 value is measured. Pre-GC A4 is drawn at visit, and once results are received Investigator or designee will call participant and advise regarding any GC dose change. This process applies to all Cohort 1-3 participants and any Cohort 4-9 participants who continue treatment in the extension period.
- Vital signs: blood pressure, pulse rate, body temperature, respiration rate, and weight
- Physical exam (abbreviated/directed)
- Suicidality Questionnaire- C-SSRS since last visit (participants aged ≥ 6 years only)
- Depression and Anxiety Questionnaires (PROMIS or SWYC depending on age of participant)
- Study drug accountability
- Assess for AEs

- Weight-based tildacerfont dose adjustment, if indicated
- For Cohort 4-9 participants, offer continued treatment in extension at Investigator's discretion, re-consent if applicable.

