3.1.2.6. Visit 6 (EOT for Cohorts 1-3) (Week 12 ±3 days)

Visit 6 will be conducted as an outpatient visit. The following activities will be performed:

- Review concomitant medications for any changes
- Pregnancy test for FOCP (urine)
- Safety labs (see [Appendix 1](#))
- Pharmacodynamics (ACTH, 17-OHP, A4, testosterone, and 11KT) drawn prior to GC dosing at approximately 8 AM (±1 hour). Fasting is not required.
- Cortisol
- Tildacerfont concentration (single sample) drawn prior to GC dosing at approximately 8 AM (±1 hour). Fasting is not required.
- GC dosing adjustments (for Cohort 1-3 patients who are continuing in the EP) to be determined after A4 value is resulted
- Urinalysis
- Vital signs: blood pressure, pulse rate, body temperature, respiration rate, and weight
- Physical exam (full)

- 12-lead ECG
- Suicidality Questionnaire- C-SSRS since last visit (participants aged 6- to 17-years only)
- Depression and Anxiety Questionnaires (PROMIS or SWYC depending on age of participant)
- Study drug accountability
- Assess for AEs

3.1.2.7. Safety Follow-up Visit Telephone Call (30 days after last dose \pm 7 days)

Approximately 30 days after the last dose of study drug (post the 12- or 4-week treatment period, depending on cohort, or post the extension), participants will have a final follow-up visit conducted by telephone. Concomitant medications and AEs will be reviewed. If any ongoing safety issues are identified, the participant may be asked to visit the clinic for additional tests, labs, or assessments.

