Weight/Efficacy Tildacerfont Dose Adjustment	X		X	X	X	X	X	X	X			
Dispense study drug	X	X	X	X	X	X	X	X	X			
Review any AEs	X	X	X	X	X	X	X	X	X	X	X	X
Study drug accountability	X	X	X	X	X	X	X	X	X	X	X	

Abbreviations: 11KT=11-ketotestosterone; A4=androstenedione; ACTH=adrenocorticotropin hormone; AEs=adverse events; ALT=alanine aminotransferase; ALP=alkaline phosphatase; AST=aspartate aminotransferase; C-SSRS=Columbia–Suicide Severity Rating Scale; ECG=electrocardiogram; EOT= end of treatment; ET=early termination; FOCP=female of childbearing potential; GC=glucocorticoid; GGT=gamma-glutamyl transferase; PD=pharmacodynamics; PROMIS= Patient Reported Outcomes Measurement Information System; 17-OHP=17-hydroxyprogesterone; SWYC=Survey of Well-being of Young Children; T=testosterone.

¹ A serum pregnancy test will be performed at Screening for FOCP only. All subsequent tests will be urine pregnancy tests

² Labs will be drawn at 8 AM (±1 h) before any morning dose of GC medication.

³ Laboratory assessments include: hematology, chemistry (including liver function tests AST, ALT, ALP, GGT, total and direct bilirubin, and total bile acids), thyroid panel. Fasting is not required.

⁴ As needed based upon any safety concerns, per Investigator discretion.

⁵ PD Samples (ACTH, 17-OHP, A4, testosterone, and 11KT). They must be drawn prior to GC dosing. Fasting is not required. Single samples for plasma concentration of tildacerfont will be drawn at all visits.

⁶ GC dose (frequency or total daily dose) may be adjusted based on A4 levels collected at each visit. If a change in GC is warranted by the A4 algorithm, sites will contact participants by telephone after receipt of results (within approximately 2 weeks) after each applicable study visit.

⁷ Urinalysis should include the following: specific gravity, pH, glucose, protein, blood, ketones, bilirubin, urobilinogen, nitrite, by dipstick. Microscopic examination should be obtained if blood or protein is abnormal.

⁸ Systolic and diastolic blood pressure, pulse rate, body temperature, and respiration rate.

⁹ The C-SSRS, to assess suicidality, is only conducted for participants aged ≥6 years.

¹⁰ PROMIS, to assess anxiety and depression, is conducted for participants aged ≥5 years.

¹¹ The SWYC to assess anxiety and depression is only conducted in Cohort 7 (and 9 if indicated) for participants ≤5 years of age.

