 In all cohorts, GC dose (frequency or total daily dose) may be adjusted based on A4 levels collected at Weeks 4 and 8 (all participants) and Week 12 (for those participants continuing in the optional EP). If a change in GC is warranted by the A4 algorithm, sites will contact participants by telephone after receipt of results (within approximately 2 weeks) after each applicable study visit.

 Urinalysis should include the following: specific gravity, pH, glucose, protein, blood, ketones, bilirubin, urobilinogen, nitrite, by dipstick. Microscopic examination should be obtained if blood or protein is abnormal. For visits in which tildacerfont is administered, urinalysis should be performed pre-dose.

 Systolic and diastolic blood pressure, pulse rate, body temperature, and respiration rate. Height will only be collected every 6 months.

 Full physical exam is performed at Visit 2, Visit 6, and ET Visit; an abbreviated/directed physical exam is performed at all other visits.

 Day 1 ECGs are conducted pre-dose. Day 14 ECG is dose independent, as participants should be at steady state.

 Historical bone age and predicted adult height calculation may be used if performed  $\leq$ 6 months prior to Screening. If no appropriate image is available, x-ray of left hand and wrist will be performed to assess bone age and calculate predicted adult height.

 The C-SSRS, to assess suicidality, is only conducted for participants aged 6 to 17 years.

 PROMIS, to assess anxiety and depression, is conducted for participants aged 5 to 17 years.

 The SWYC to assess anxiety and depression is only conducted in Cohort 3 participants  $\leq$ 5 years of age.

 A 12-week supply of study drug will be dispensed at Visit 2 (Day 1). Participants should bring study drug to all visits for accountability. Upon receipt of study drug, the pharmacy will hold/store two doses to ensure that in-clinic dosing can occur at Visit 3 (Week 2) in the event a participant does not bring study drug to the visit.

 Cohorts 1 and 2 dosing:

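### In the Cohorts 4-9 extension, the glucocorticoid algorithm can call for a dose reduction at Week 96 (EOT), where no further tildacerfont and no later A4 are scheduled

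*SAP*

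**What the plan says.** In SAP Table 11 the row "A4-based GC dose adjustment" is marked at every scheduled visit from Week 4 to Week 96 (EOT) and is blank at Early Termination and Safety Follow-up. Protocol Appendix 4 has the same marks. In both, the row "Dispense study drug" stops at Week 84, and tildacerfont dose adjustment is blank at Week 96.

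Footnote 6 of both tables reads "GC dose (frequency or total daily dose) may be adjusted based on A4 levels collected at each visit". Protocol 5.3.1.2 and SAP 5.2.2 give the same rule for the extension. None of these texts asks whether tildacerfont continues. The algorithm (Protocol 5.3.1.2; SAP Table 2) lowers GC when A4 is at or below ULN, holds it up to 1.5x ULN, and raises it above that. Changes are telephoned within about 2 weeks of the visit.

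The main-period EOT visits are treated differently. At Week 4, Protocol 3.1.2.4 says "This process applies to all Cohort 1-3 participants and any Cohort 4-9 participants who continue treatment in the extension period". At Week 12, Protocol 3.1.2.6 says "GC dosing adjustments (for Cohort 1-3 patients who are continuing in the EP) to be determined after A4 value is resulted". The footnotes to SAP Tables 8 and 10 carry the same limit: "Week 12 (for those participants continuing in the optional EP" and "based on A4 levels collected at Week 4 (for those participants continuing in the optional EP".

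After Week 96 the only scheduled contact is a telephone call about 30 days after the last dose. Footnote 4 of SAP Table 11 makes pharmacodynamic samples at that point "As needed based upon any safety concerns, per Investigator discretion".

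**The concern.** Protocol 1.1.2 says that CAH patients need GC above physiologic doses to control androgens. Protocol 1.1.3 says that tildacerfont may let them keep normal androgens on roughly replacement doses. A normal A4 measured on drug may therefore owe something to the drug. If GC is lowered on that value just as the drug ends, the participant may lose two sources of androgen control together.

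No scheduled sample would show a later rise in A4. Four of the six cohorts are pediatric, and Protocol 1.1.2 links high androgens in children to skeletal maturation and reduced adult height. This is a matter of participant care during the extension, not of estimation.

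**Working it through.** No sample-size or error-rate figure is involved. The check aligns the schedule rows with their column headings and compares the texts.

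**1. Marks in the extension schedules**

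| Schedule | Cohorts | GC adjustment, Week 96 | Dispensing, Week 96 | GC adjustment, Early Termination |
|---|---|---|---|---|
| SAP Table 11 | 4-9 | marked | blank | blank |
| Protocol Appendix 4 | 4-9 | marked | blank | blank |
| SAP Table 9 | 1-3 | blank | blank | blank |
| Protocol Appendix 2 | 1-3 | marked | marked | blank |

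In SAP Table 11 and Protocol Appendix 4, GC adjustment has 10 marks (Weeks 4 to 96), dispensing 9 (Weeks 4 to 84) and tildacerfont dose adjustment 8 (none at Weeks 8 or 96). The two documents agree cell by cell on these rows, so a table-reading error is unlikely. For Cohorts 1-3 the protocol and SAP disagree with each other, but each keeps GC adjustment and dispensing together at Week 96. Only the Cohorts 4-9 schedules separate them.

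**2. Drug supply**

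Protocol 3.1.3 provides about 12 weeks of drug per dispensing visit. The last marked dispensing is Week 84, and 84 + 12 = Week 96. Extension visits have a window of ±2 weeks, so the gap between the Week 84 and Week 96 visits can run from 94 - 86 = 8 weeks to 98 - 82 = 16 weeks. The Week 96 A4 is on drug when the visit is on time or early. After a long gap it may already be off drug, and the concern then weakens.

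**3. What follows if the rule is applied**

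- A4 at or below ULN at Week 96 points to a GC reduction.
- The call comes up to about 14 days after the visit.
- The follow-up call is 30 ± 7 days after the last dose, that is day 23 to day 37 (Protocol 3.1.2.7).
- As an illustration, suppose the last dose is on the visit day and the GC call is as late as allowed. Follow-up then falls 23 - 14 = 9 to 37 - 14 = 23 days after the GC change.
- A4 samples scheduled after Week 96: none.

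**4. Default and safeguards**

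Protocol 5.3.1.2 asks an investigator who does not intend to follow the algorithm at a visit to contact the Medical Monitor. It also asks for discussion with the Medical Monitor before GC goes below physiologic levels. So an investigator who holds GC because the drug is ending is asked to call, while one who reduces to a dose still at or above physiologic level is not.

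**5. How many participants**

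Planned maximum in Cohorts 4-9: 15 adults + 30 children = 45. Those exposed are the subset who enter the extension, reach Week 96, have A4 at or below ULN and are given a reduction. The documents supply none of these rates.

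**The case against.** The strongest reply is that the stop date is not settled. Protocol 3.1.3 speaks of completing two years on treatment, about 104 weeks, and of supplying drug at each visit. Protocol Appendix 2 marks dispensing at Week 96, although that visit is also labelled EOT. This stands: a reader might infer that tildacerfont certainly ends at Week 96, and the documents do not support that. They do show that the schedule governing Cohorts 4-9 plans no drug beyond that visit.

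The second reply is that the rule is permissive and supervised. The algorithm is guidance. The Sponsor may contact the site after any extension visit to confirm GC changes, and follow-up can lead to recall for laboratory tests. The Pharmacy Manual, which Protocol 5.3.1.2 cites for further GC guidance, was not available and might address the end of treatment. All of this lowers the risk. It does not reverse the default described in the working.

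Third, the reason for the main-period condition is not stated. It may be operational, since participants who leave have no further study visits. The blank Early Termination cells are equally unexplained. One should not infer that the sponsor recognised this hazard and overlooked it here. The point needs only that the condition is present at the main-period EOT visits and absent at this one.

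Fourth, it is tempting to set the 2-week GC call beside the 2-week tildacerfont washout in exclusion criterion 9 and conclude that the drug effect has gone by then. That criterion concerns eligibility. It does not say when the effect ends, and the comparison should not be made.

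**Conclusion.** The point holds as a conduct and safety gap of moderate weight. For Cohorts 4-9, both documents allow an A4-driven GC reduction at the extension EOT visit with no condition that tildacerfont continues, no drug scheduled beyond the visit and no later A4 scheduled.

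The conclusion assumes that Appendix 4 and SAP Table 11 are followed as printed, that the Week 96 A4 is drawn on drug, and that no unseen document sets an end-of-treatment instruction. Its size is unknown beyond the ceiling of 45 planned participants.

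A reader might also infer that a trial result is biased. The documents do not support that: no main-period analysis uses Week 96, and SAP 4 leaves the extension analysis to a separate SAP, which was not available.

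**What to change.** In Protocol 5.3.1.2 and footnote 6 of Protocol Appendix 4, state that at the extension EOT visit a GC reduction under the algorithm applies only if tildacerfont continues, while maintaining or increasing GC remains available. Mirror the sentence in SAP 5.2.2 and footnote 6 of SAP Table 11. The protocol text is the part that governs site conduct.

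At the same time, reconcile the Week 96 GC and dispensing marks across Protocol Appendices 2 and 4 and SAP Tables 9 and 11, and settle them against the two-year target and the each-visit supply in Protocol 3.1.3. Keeping the Week 96 GC mark for Cohorts 4-9 is sensible, so that an A4 above 1.5x ULN can still prompt an increase.

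The cost is a small protocol amendment with the IRB approval that Protocol 9.10 requires, and possibly a slightly lower final GC-reduction rate. The added sentence needs no new visit or sample.
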